APPENDIX 2. PARTIAL DATE CONVENTIONS

Imputed dates will NOT be presented in the listings.

ALGORITHM FOR PRIOR / ACTIVE MEDICAL HISTORY, SURGERIES AND PROCEDURES

Partial date to be imputed as:

Start date	Earliest possible date	first day of month if day unknown or 1 st January if day and month are unknown
Stop date	Latest possible date	last day of month if day unknown or 31 st December if day and month are unknown, if not resulting in a date later than the date of subject's death. In the latter case the date of death will be used for imputation.

General rules:

- If stop date < screening date, assign as prior
- If stop date >= screening date and start date <= end of treatment, assign as concomitant
- If stop date >= screening date and start date > end of treatment, assign as post Treatment

If Missing stop date: (Rules 2)

- If stop date is missing could never be assumed as prior
- If start date <= end of treatment, assign as concomitant
- If start date > end of treatment, assign as post treatment

If Missing Start date: (Rules 3)

- If stop date < screening date, assign as prior
- If stop date >= screening date, assign as concomitant
- Cannot be assigned as 'post treatment'

Document: \\ieedc-vnasc01\BIOSdata\Boehringer_Ingelheim\BI_695501\NVA96252\Biostatistics\Documentation\SAP\BI1297.4 SAP FINAL v4.0_22MAY2019.docx

Author: Version Number: Final V4.0
Version Date: 22MAY2019

Template No: CS_TP_BS016 Revision 5
Effective Date: 01Apr2018

Reference: CS_WI_BS005

START DATE	STOP DATE	ACTION
Known	Known	General rules
	Partial	General rules
	Missing	Rules 2
Partial	Known	General rules
	Partial	General rules
	Missing	Rules 2
Missing	Known	Rules 3
	Partial	Rules 3
	Missing	Assign as concomitant

ALGORITHM FOR TREATMENT EMERGENCE OF ADVERSE EVENTS:

START DATE	STOP DATE	ACTION
Known	Known Partial Missing	If start date < trial med start date or start date > trial med stop date +70 days, then not TEAE If start date >= trial med start date and start date <= trial med stop date +70 days, then TEAE
Partial, but known components show that it cannot be on or after trial med start date	Known Partial Missing	Not TEAE
Partial, could be on or after trial med start date and prior to trial med stop date + 70 days	Known	Impute start date as earliest possible date, (i.e., first day of month if day unknown or 1st January if day and month are unknown), except if only day is missing and month and year of start date are the same as for trial med start date or if day and month are missing and year of start date is the same as for trial med start date. In the latter cases, the trial med start date will be used for the imputation.

Document: \\ieedc-vnasc01\BIOSdata\Boehringer_Ingelheim\BI_695501\NVA96252\Biostatistics\Documentation\SAP\BI1297.4 SAP FINAL v4.0_22MAY2019.docx

Author: Version Number: Final V4.0
Version Date: 22MAY2019

Template No: CS_TP_BS016 Revision 5
Effective Date: 01Apr2018

Reference: CS_WI_BS005

START DATE	STOP DATE	ACTION
		If start date \leq stop date, then: If stop date $<$ trial med start date, then not TEAE If start date $>$ trial med end date +70 days, then not TEAE If stop date \geq trial med start date and start date \leq trial med end date +70 days, then TEAE If start date $>$ stop date, then: Consider the start date as Missing and apply the algorithms for missing start date
	Partial	Impute start date as above. Impute stop date as latest possible date (i.e., last day of month if day unknown or 31 st December if day and month are unknown), if not resulting in a date later than the date of subject's death. In the later case the date of death will be used for imputation. If start date \leq stop date, then: If stop date $<$ trial med start date, then not TEAE If start date $>$ trial med end date +70 days, then not TEAE If stop date \geq trial med start date and start date \leq trial med end date +70 days, then TEAE If start date $>$ stop date, then: Consider the start and stop dates as Missing and apply the algorithms for missing start date
	Missing	Assumed TEAE
Missing	Known	If stop date $<$ trial med start date, then not TEAE If stop date \geq trial med start date, then TEAE
	Partial	Impute stop date as latest possible date (i.e. last day of month if day unknown or 31 st December if day and month are unknown), then: If stop date $<$ trial med start date, then not TEAE If stop date \geq trial med start date, then TEAE

Document: \\ieedc-vnasc01\BIOSdata\Boehringer_Ingelheim\BI_695501\NVA96252\Biostatistics\Documentation\SAP\BI1297.4 SAP FINAL v4.0_22MAY2019.docx

Author: Version Number: Final V4.0
 Version Date: 22MAY2019

Template No: CS_TP_BS016 Revision 5
 Effective Date: 01Apr2018

Reference: CS_WI_BS005

START DATE	STOP DATE	ACTION
	Missing	Assumed TEAE

ALGORITHM FOR PRIOR / CONCOMITANT MEDICATIONS:

Partial date to be imputed as:

Start date	Earliest possible date	first day of month if day unknown or 1 st January if day and month are unknown
Stop date	Latest possible date	last day of month if day unknown or 31 st December if day and month are unknown, if not resulting in a date later than the date of subject's death. In the latter case the date of death will be used for imputation.

General rules:

- If stop date < trial med start date, assign as prior
- If stop date >= trial med start date and start date <= end of treatment, assign as concomitant
- If stop date >= trial med start date and start date > end of treatment, assign as post treatment

If Missing stop date: (Rules 2)

- If stop date is missing could never be assumed a prior medication
- If start date <= end of treatment, assign as concomitant
- If start date > end of treatment, assign as post treatment

If Missing Start date: (Rules 3)

- If stop date < trial med start date, assign as prior
- If stop date >= trial med start date, assign as concomitant
- Cannot be assigned as 'post treatment'

START DATE	STOP DATE	ACTION
Known	Known	General rules

Document: \\ieedc-vnasc01\BIOSdata\Boehringer_Ingelheim\BI_695501\NVA96252\Biostatistics\Documentation\SAP\BI1297.4 SAP FINAL v4.0_22MAY2019.docx

Author: Version Number: Final V4.0
Version Date: 22MAY2019

Template No: CS_TP_BS016 Revision 5
Effective Date: 01Apr2018

Reference: CS_WI_BS005

Copyright © 2009, 2010, 2012, 2016, 2018 All rights reserved. The contents of this document are confidential and proprietary to Holdings Inc. and its subsidiaries. Unauthorized use, disclosure or reproduction is strictly prohibited.

Statistical Analysis Plan

START DATE	STOP DATE	ACTION
	Partial	General rules
	Missing	Rules 2
Partial	Known	General rules
	Partial	General rules
	Missing	Rules 2
Missing	Known	Rules 3
	Partial	Rules 3
	Missing	Assign as concomitant

Document: \\ieedc-
vnasc01\BIOSdata\Boehringer_Ingelheim\BI_695501\NVA96252\Biostatistics\Documentation\S
AP\BI1297.4 SAP FINAL v4.0_22MAY2019.docx

Author: Version Number: Final V4.0
Version Date: 22MAY2019

Template No: CS_TP_BS016 Revision 5
Effective Date: 01Apr2018

Reference: CS_WI_BS005

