16.1.1. ADVERSE EVENT SPECIFIC DERIVATION

16.1.1.1. Treatment Emergent Adverse Event

Treatment-Emergent Adverse Events (TEAEs) are defined as AEs that started or worsened on or after the first dose of trial medication and prior to the last date of trial medication + 10 weeks (70 days) inclusive.

There are two specific periods of interest:

Period 1 Treatment-Emergent Adverse Events (P1 TEAEs) are defined as AEs that started or worsened on or after the first dose of trial medication and prior to the date of Week 24 visit or within 10 weeks (70 days, inclusive) after the last dose of IMP for patients who discontinued the treatment before Week 24.

Period 2 Treatment-Emergent Adverse Events (P2 TEAEs) are defined as AEs that started or worsened on Week 24 visit and prior to or on the Week 56 visit or within 10 weeks (70 days, inclusive) after the last dose of IMP for patients discontinuing treatment prior to Week 46.

Non-TEAEs will be classified as "Screening" if AE start date is strictly prior to the first injection date. Non-TEAEs will be classified as "Post treatment" if AE start date is strictly after the last injection date + 70 days.

See APPENDIX 2 for handling of partial dates for AEs. In the case where it is not possible to define an AE as treatment-emergent or not, the AE will be classified by the worst case, i.e., treatment-emergent in the period of the last injection of trial medication.

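### SAP Appendix 2 counts as treatment-emergent an AE with a year-only onset whose month-only stop shows that it ended before the first dose

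*SAP*

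**What the plan says.** SAP 16.1.1.1 sets the definition: "Treatment-Emergent Adverse Events (TEAEs) are defined as AEs that started or worsened on or after the first dose of trial medication", up to 70 days after the last dose. It adds a fallback: "In the case where it is not possible to define an AE as treatment-emergent or not, the AE will be classified by the worst case", that is, "treatment-emergent in the period of the last injection of trial medication".

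The algorithm for treatment emergence in SAP Appendix 2 handles incomplete dates. The row at issue covers onsets described as "Partial, could be on or after trial med start date and prior to trial med stop date + 70 days". Its steps are:

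- A partial onset goes to its earliest possible date, except where its month and year (day missing) or its year (day and month missing) match the first dose. For these the row says "In the latter cases, the trial med start date will be used for the imputation".
- For a partial stop: "Impute stop date as latest possible date (i.e., last day of month if day unknown", or 31 December if the month is also unknown.
- If the imputed start is after a **known** stop: "Consider the start date as Missing and apply the algorithms for missing start date".
- If the imputed start is after a **partial** stop: "Consider the start and stop dates as Missing and apply the algorithms for missing start date".

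The missing-start rows then apply. With a known or partial stop before the first dose, the event is not a TEAE. With the stop also missing, it is assumed to be one.

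**The concern.** In the partial-stop row the stop is discarded because it conflicts with an onset that the algorithm itself moved to the first-dose date. The conflict is produced by the imputation and need not exist in the recorded data. The discarded stop is the one piece of information that settles the classification: if its latest possible value is before the first dose, the event neither started nor worsened on treatment. Worsening offers no way round this, because SAP 16.1 gives a worsening its own entry with its own start date.

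The case can arise because AEs are collected from informed consent (Protocol Flow Chart A, footnote 9), so screening events pass through this algorithm. At stake are the TEAE counts and the risk ratios and risk differences computed from them (SAP 16.1.1.2 and 16.1.1.3).

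**Working it through.** **1. One event through three rows.** The calendar dates are illustrative. First dose 15 June 2018; the event ended in May 2018.

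| Recorded onset | Recorded stop | Imputed start | Stop used | Rule applied | Result |
|---|---|---|---|---|---|
| 2018 only | May 2018 | 15 Jun 2018 | 31 May 2018 | start after partial stop: both set to missing | TEAE |
| 2018 only | 28 May 2018 | 15 Jun 2018 | 28 May 2018 | start after known stop: only start set to missing | not TEAE |
| missing | May 2018 | none | 31 May 2018 | missing start, partial stop | not TEAE |

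The latest possible stop in the first line is 15 days before the first dose (31 May to 15 June). Recording the onset year gives a worse answer than recording no onset.

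**2. The row's own safeguard cannot work.** For imputed start on or before stop, the row says that a stop before the first dose means not a TEAE. But every onset that enters the row is imputed to the first-dose date or later. An onset in the first-dose month or year goes to the first dose, and a later month or year goes to a date after it. So start on or before stop implies stop on or after first dose, and the check never fires (0 hits when the rules were coded and enumerated).

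**3. Which recorded dates reach the branch without contradicting each other.**

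- Onset month recorded and equal to the first-dose month: a stop that month or later has a latest possible date on or after the first dose, so the branch is not reached. A stop in an earlier month contradicts the onset.
- Onset month recorded and earlier: an earlier row already makes the event not a TEAE.
- Onset year only, equal to the first-dose year, stop in an earlier month of that year: the branch is reached and the dates are compatible.

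Only the third pattern is both coherent and misclassified.

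**4. Enumeration of date patterns.** Inputs: weekly first-dose dates across 2017 and 2018 (assumed; 105 dates), with all month-only and year-only starts and stops from 2016 to 2020.

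- Combinations reaching the branch: 53,044 = 41,954 with the stop wholly before first dose + 11,090 with a later stop.
- Of the 41,954, all become TEAEs under the present text. Those with compatible dates number 585, which is the sum over the 105 dates of (first-dose month − 1). The other 41,954 − 585 = 41,369 have contradictory dates.
- Comparator: a known stop before first dose gives not TEAE in 112,292 of 112,292 combinations.

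**5. How often the coherent pattern reaches the branch.** Assume first dose on any day of 2018, onset and stop 1 to 28 days before it (screening maximum, Protocol 3.1), onset in 2018 but recorded by year only, stop recorded by month, and equal weights.

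- Onset/stop pairs per first-dose day: 28 × 29 / 2 = 406. For the first 28 days of January, requiring onset in 2018 leaves Σ k(k−1)/2 for k = 1 to 28, which is 3,654. Total: 337 × 406 + 3,654 = 140,476.
- Pairs with the stop in an earlier month: for first dose on day j of the month, (29−j)(30−j)/2. The sum over j = 1 to 28 is 4,060 per month. February to December: 11 × 4,060 = 44,660.
- Share: 44,660 / 140,476 = 31.8%. In the other 68.2% the stop month is the first-dose month, where treatment emergence cannot be excluded and the worst-case answer is appropriate.

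**The case against.** The strongest objection concerns the obvious repair, which is to copy the known-stop wording into this row and always keep the stop. A reader might infer that this costs nothing. It does not. Take first dose 15 June 2018, onset August 2018, stop May 2018. The present text discards both dates and returns TEAE. Keeping the stop would return not TEAE for an event whose recorded onset month lies wholly after the first dose, probably because of an error in the stop date. That is anti-conservative and runs against the worst-case principle in 16.1.1.1. Step 4 shows that a blanket change would also reclassify 41,369 contradictory patterns to correct 585 coherent ones. This objection stands and determines the form of the fix.

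The second objection is rarity, and it also stands. Protocol 8.3.1 lists AE onset date as mandatory, screening lasts at most 28 days, and abnormalities that pre-date inclusion count as baseline conditions (Protocol 5.3.6.2). A year-only onset would have to survive data cleaning for an event in a known window of about four weeks.

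Third, the consequence is limited. Safety analysis is descriptive (Protocol 7.3.4, SAP 16), listings show TEAEs and non-TEAEs, and screening events precede randomization, so no systematic imbalance between arms is expected in overall TEAEs.

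What does not stand is a defence of the rule as a deliberate worst case. That principle covers events that cannot be classified. Here the recorded stop month classifies the event.

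**Conclusion.** The rule is wrong as written for one narrow pattern: a year-only onset in the first-dose year with a month-only stop in an earlier month of that year. Every such event becomes a TEAE against the definition in 16.1.1.1 and against the two neighbouring rows. It is a minor correction. The documents give no count of partial dates, so the effect on TEAE rates cannot be computed; it should be small.

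Two stronger readings are tempting but unsupported.

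- A reader might take 31.8% as the share of AEs affected. It is conditional on the double-partial pattern, rests on equal weighting of calendar dates, and says nothing about how often the pattern occurs.
- A reader might infer that such events will be reported as post-switch events on BI 695501. Appendix 2 assigns no period, and the last-injection fallback in 16.1.1.1 is written for events that cannot be classified. If the fallback were applied, a completer's event would fall in Period 2, but an event in a patient who stopped before Week 24 would fall in Period 1. Only patients randomized to Humira switch at all. Placement in Period 2 is therefore a possible consequence and not an established one.

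**What to change.** In the partial-start, partial-stop row of Appendix 2, split the case where the imputed start is after the imputed stop:

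1. If the start was set to the first-dose date by the same-month or same-year exception, the imputed (latest possible) stop is before the first dose, and the recorded onset components do not themselves lie after the stop, keep the imputed stop and apply the missing-start, partial-stop row. The result is not TEAE. By step 3, only the same-year exception meets all three conditions.
2. If the recorded onset itself lies after the recorded stop, leave the present worst-case rule and query the record. This takes precedence over item 1, so onset June 2018 with stop May 2018 stays a TEAE pending the query.

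In step 4 this reclassifies the 585 compatible patterns and leaves the 41,369 contradictory ones, and the 11,090 with a later stop, as they are.

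The cost is a sentence or two in the appendix, one extra condition in the program and a query for any contradictory record. It would also help to state in 16.1.1.1 which period an event with no usable onset receives when Appendix 2 has already assumed it to be treatment-emergent.

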APPENDIX 3. EMA SOC ORDER FOR PRESENTATION OF THE AE IN THE TABLES.**Order System Organ Class**

- 0 Uncoded
- 1 Infections and infestations
- 2 Neoplasms benign, malignant and unspecified (incl cysts and polyps)
- 3 Blood and lymphatic system disorders
- 4 Immune system disorders
- 5 Endocrine disorders
- 6 Metabolism and nutrition disorders
- 7 Psychiatric disorders
- 8 Nervous system disorders
- 9 Eye disorders
- 10 Ear and labyrinth disorders
- 11 Cardiac disorders
- 12 Vascular disorders
- 13 Respiratory, thoracic and mediastinal disorders
- 14 Gastrointestinal disorders
- 15 Hepatobiliary disorders
- 16 Skin and subcutaneous tissue disorders
- 17 Musculoskeletal and connective tissue disorders
- 18 Renal and urinary disorders
- 19 Pregnancy, puerperium and perinatal conditions
- 20 Reproductive system and breast disorders
- 21 Congenital, familial and genetic disorders
- 22 General disorders and administration site conditions
- 23 Investigations
- 24 Injury, poisoning and procedural complications
- 25 Surgical and medical procedures
- 26 Social circumstances
- 27 Product issues

Document: \\ieedc-
vnasc01\BIOSdata\Boehringer_Ingelheim\BI_695501\NVA96252\Biostatistics\Documentation\S
AP\BI1297.4 SAP FINAL v4.0_22MAY2019.docx

Author: Version Number: Final V4.0
Version Date: 22MAY2019

Template No: CS_TP_BS016 Revision 5
Effective Date: 01Apr2018

Reference: CS_WI_BS005

Document: \\ieedc-
vnasc01\BIOSdata\Boehringer_Ingelheim\BI_695501\NVA96252\Biostatistics\Documentation\S
AP\BI1297.4 SAP FINAL v4.0_22MAY2019.docx

Author: Version Number: Final V4.0
Version Date: 22MAY2019

Template No: CS_TP_BS016 Revision 5 Reference: CS_WI_BS005
Effective Date: 01Apr2018

APPENDIX 5. LABORATORY ASSESSMENTS

Laboratory parameter	SI unit	US unit
Serum chemistry		
Creatinine	umol/L	mg/dL
Alkaline phosphatase	IU/L	U/L
Aspartate aminotransferase (AST)	U/L	U/L
Alanine aminotransferase (ALT)	U/L	U/L
Gamma glutamyl transpeptidase (GGT)	U/L	U/L
Lactic dehydrogenase	U/L	U/L
Lipase	U/L	U/L
Amylase	U/L	U/L
IgE	kUL	kUL
IgG	g/L	ng/dL
Total bilirubin	umol/L	mg/dL
Direct bilirubin	umol/L	mg/dL
Glucose	mmol/L	mg/dL
Total cholesterol	mmol/L	mg/dL
Total protein	g/L	g/dL
Sodium	mmol/L	mEq/L
Potassium	mmol/L	mEq/L
Chloride	mmol/L	mEq/L
Calcium	mmol/L	mg/dL
Albumin	g/L	g/dL
Bicarbonate	mmol/L	nEq/L
Uric acid	umol/L	mg/dL
High density lipoprotein cholesterol	mmol/L	mg/dL
Calculated low density lipoprotein	mmol/L	mg/dL
Triglycerides	mmol/L	mg/dL
Hematology		
Hemoglobin	g/L	g/dL
Hematocrit	V/V	%
Erythrocyte	10 ¹² /L	10 ⁶ /uL
Platelets	10 ⁹ /L	10 ³ /uL
White blood cells	10 ⁹ /L	10 ³ /uL
Lymphocytes	10 ⁹ /L	10 ³ /uL
Neutrophils	10 ⁹ /L	10 ³ /uL

Document: \\ieedc-
vnasc01\BIOSdata\Boehringer_Ingelheim\BI_695501\NVA96252\Biostatistics\Documentation\S
AP\BI1297.4 SAP FINAL v4.0_22MAY2019.docx

Author: Version Number: Final V4.0
Version Date: 22MAY2019

Template No: CS_TP_BS016 Revision 5
Effective Date: 01Apr2018

Reference: CS_WI_BS005

Laboratory parameter	SI unit	US unit
Reticulocyte	%	%
Eosinophils	%	%
Basophils	%	%
Monocytes	%	%
Partial thromboplastin time	seconds	seconds
Prothrombin time	seconds	seconds
Fibrinogen	g/L	ng/dL
Urinalysis		
Protein	-	-
Glucose	-	-
Nitrite	-	-
Ketone	-	-
Urobilinogen	-	-
Bilirubin	-	-
Erythrocyte	-	-
Leukocyte	-	-
pH	-	-

Document: \\ieedc-
vnasc01\BIOSdata\Boehringer_Ingelheim\BI_695501\NVA96252\Biostatistics\Documentation\S
AP\BI1297.4 SAP FINAL v4.0_22MAY2019.docx

Author: Version Number: Final V4.0
Version Date: 22MAY2019

Template No: CS_TP_BS016 Revision 5
Effective Date: 01Apr2018

Reference: CS_WI_BS005
